## 14 Statistical Considerations

### 14.1 General Considerations

Parameter estimates and relevant summary statistics will be reported for both efficacy and safety outcomes. Continuous variables will be summarized by means, medians, minima, maxima and standard deviations. Categorical variables will be summarized by frequencies and percentages. Missing data will not be imputed. Additional exploratory analysis will be conducted when appropriate. Changes from the analysis plan will not require an amendment to the protocol unless it changes a significant feature in the protocol. The statistical analysis methods are outline below.

### 14.2 Study Design

This is a single arm pilot study. No randomization or blinding is involved.

### 14.3 Analysis Population

#### 14.3.1 Enrolled Population

The enrolled population comprises all patients who meet the eligibility criteria and are registered onto the study.

### 14.3.2 Safety Population

The safety population comprises all patients who have received at least one dose of the study medication. This set will be used for safety analysis.

### 14.3.3 Efficacy Population

The efficacy population comprises all patients who have received at least one dose of the study medication, have been evaluated for the primary endpoint, and have no significant protocol violations. This population will be used for efficacy analysis.

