### **Thromboembolic Events**

Thromboembolic complications are frequent in cancer patients due to procoagulant changes induced by the malignancy or anticancer therapy including inhibitors of VEGF pathways. Deep vein thrombosis and PE have been observed in clinical studies with cabozantinib; including fatal events (please refer to the Investigator's Brochure). The risk of hemorrhage in cabozantinib-treated subjects with brain metastases has not been thoroughly analyzed. The incidence of CNS hemorrhage events in a study of subjects with GBM was higher than observed in general population of subjects with cancer treated with cabozantinib. Based on this observation, any subjects on this study will be taken off study if DVT occurs and anticoagulation is required to reduce the risk of hemorrhage of subjects on study. Subjects who require anticoagulation for any reason will be considered off-study.

Subjects with DVT who may require anticoagulant therapy will be taken off study.

Arterial thrombotic events (eg, transient ischemic attack, myocardial infarction) have been observed in studies with cabozantinib. Subjects should be evaluated for preexisting risk factors for arterial thrombotic events such as diabetes mellitus, hyperlipidemia, hypertension, coronary artery disease, history of tobacco use, and cardiac or thromboembolic events that occurred before initiation of study treatment. Cabozantinib treatment should be discontinued in subjects who develop an acute myocardial infarction, cerebral infarction or any other clinically relevant arterial thromboembolic complication.

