## 12. Study Withdrawal/Discontinuation

Reasons for a patient to not complete the study:

- a) Death
- b) Disease progression
- c) Lost to follow-up
- d) Entry into another therapeutic study
- e) Patient request to withdraw from clinical trial
- f) Manufacturing limitations on drug supplies
- g) Adverse events requiring removal from study
- h) Pregnancy
- i) Breastfeeding
- j) Non-compliance that in the opinion of the investigator does not allow for ongoing participation
- k) Physician determines that it is not in the patient's best interest
- l) Subject develops DVT and requires anticoagulation therapy

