#### Progressive Disease (PD):

Progression is defined by any of the following:  $\geq 25\%$  increase in sum of the products of perpendicular diameters of enhancing lesions (compared with baseline if no decrease) on stable or increasing doses of corticosteroids; a significant increase in T2/FLAIR non-enhancing lesions on stable or increasing doses of corticosteroids compared with baseline scan or best response after initiation of therapy, not due to comorbid events; the appearance of any new lesions; clear progression of non-measurable lesions; or definite clinical deterioration not attributable to other causes apart from the tumor, or to decrease in corticosteroid dose. Failure to return for evaluation as a result of death or deteriorating condition should also be considered as progression.

Increase in corticosteroid dose alone, in the absence of clinical deterioration related to tumor, will not be used as a determinant of progression. Patients with stable imaging studies whose corticosteroid dose was increased for reasons other than clinical deterioration related to tumor do not qualify for stable disease or progression. They should be observed closely. If their corticosteroid dose can be reduced back to baseline, they will be considered as having stable disease; if further clinical deterioration related to tumor becomes apparent, they will be considered to have progression. The date of progression should be the first time point at which corticosteroid increase was necessary.

The definition of clinical deterioration is left to the discretion of the treating physician, but it is recommended that a decline in the KPS from 100 or 90 to 70 or less, a decline in KPS of at least 20 from 80 or less, or a decline in KPS from any baseline to 50 or less, for at least 7 days, be considered neurologic deterioration unless attributable to comorbid events or changes in corticosteroid dose. Similarly, a decline in the Eastern Cooperative Oncology Group and WHO performance scores from 0 or 1 to 2 or 2 to 3 would be considered neurologic deterioration.

Patients with non-measurable enhancing disease whose lesions have significantly increased in size and become measurable (minimal bidirectional diameter of  $\geq 10$  mm and visible on at least two axial slices that are preferably, at most, 5 mm apart with 0-mm skip) will also be considered to have experienced progression. The transition from a

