#### 14.6 Efficacy Analysis

The efficacy set will be used for all the efficacy analysis. For the primary efficacy aim of the disease control rate (CR, PR, or SD for at least 6 months), an estimate will be determined along with the corresponding exact 95% binomial confidence interval. A similar analysis will be done for the secondary objective of objective response rate (CR, PR).

For PFS and OS, the median and their corresponding two-sided 95% confidence intervals will be calculated using the Kaplan-Meier method. Estimates and 95% confidence intervals will also be provided for 6 and 12 months.

A listing of the patients who used corticosteroid will be provided.

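### The only efficacy set leaves out treated patients who were not evaluated or who had a significant protocol violation, so disease control and response rates can be inflated

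*Combined protocol and SAP*

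**What the plan says.** Section 14.3 defines three populations.

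- **Enrolled (14.3.1):** eligible, registered patients. No analysis is assigned to this set.
- **Safety (14.3.2):** "The safety population comprises all patients who have received at least one dose of the study medication". It is assigned to the safety analysis only.
- **Efficacy (14.3.3):** treated patients who also "have been evaluated for the primary endpoint, and have no significant protocol violations. This population will be used for efficacy analysis".

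Section 14.6 then states: "The efficacy set will be used for all the efficacy analysis". That covers DCR (the primary efficacy aim, reported with an exact 95% binomial interval), ORR, PFS and OS. Section 14.1 adds: "Missing data will not be imputed". Section 14 defines neither being evaluated for the primary endpoint nor a significant violation, and it plans no efficacy analysis in all treated patients.

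Section 13, under Progressive Disease, has one relevant rule: "Failure to return for evaluation as a result of death or deteriorating condition should also be considered as progression". Section 14 does not refer to it.

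**The concern.** Membership of the efficacy set depends on what happens after the first dose. DCR requires CR, PR, or SD for at least 6 months. A treated patient with no qualifying assessment cannot be recorded as a success, so removing that patient shrinks the denominator and leaves the numerator unchanged. The trial is single-arm and open-label, and both conditions are undefined, so who is left out can be decided once outcomes are known.

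DCR is the primary efficacy endpoint. Section 17 says a consortium asked for more pilot response data before considering a larger trial, so the reported rate is the main product of this study. With about 11 patients, whether a few early leavers count as failures or disappear changes that rate noticeably.

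**Working it through.** **1. Can a treated patient be left unevaluated?** The study schedule in Section 7 places the first on-treatment MRI at Day 28 of Cycle 3, which is 3 × 28 = day 84. Section 5 requires a life expectancy of only 2 months, which is shorter. Several routes off study need no progression. Section 12 lists withdrawal, loss to follow-up, non-compliance and "Adverse events requiring removal from study". The thromboembolic text in Section 7.2 adds "Subjects who require anticoagulation for any reason will be considered off-study". The schedule has an MRI in its Completion of Study column, but the plan does not say whether early leavers have that scan or whether it makes them evaluated.

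**2. The plan's own figures.** Section 14.4 gives the chance of at least one event with n = 10, which is 1 − (1 − p)^10. For p = 0.05, 0.10, 0.15, 0.20, 0.25 and 0.30 this gives 0.401, 0.651, 0.803, 0.893, 0.944 and 0.972, matching the printed 0.40, 0.65, 0.80, 0.89, 0.94 and 0.97. At p = 0.15, an efficacy set of 9, 8 or 7 lowers the 0.80 to 0.768, 0.728 or 0.679.

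**3. Effect on DCR or ORR.** Section 6 plans 11 patients; assume all are treated. Let s be the number of successes and d the number dropped, none of them a success.

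- Counting unevaluated patients as non-successes: s/11.
- Efficacy set as written: s/(11 − d).
- Ratio, for s ≥ 1: 11/(11 − d) = 11/10 = 1.10, 11/9 = 1.22, 11/8 = 1.38 for d = 1, 2, 3.

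The exact 95% limits are the 2.5% point of Beta(s, n − s + 1) and the 97.5% point of Beta(s + 1, n − s). Entries are percentages.

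| s | d = 0, n = 11 | d = 1, n = 10 | d = 2, n = 9 | d = 3, n = 8 |
|---|---|---|---|---|
| 1 | 9.1 (0.2–41.3) | 10.0 (0.3–44.5) | 11.1 (0.3–48.2) | 12.5 (0.3–52.7) |
| 2 | 18.2 (2.3–51.8) | 20.0 (2.5–55.6) | 22.2 (2.8–60.0) | 25.0 (3.2–65.1) |
| 3 | 27.3 (6.0–61.0) | 30.0 (6.7–65.2) | 33.3 (7.5–70.1) | 37.5 (8.5–75.5) |

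With three successes the upward shift is 2.7, 6.1 or 10.2 percentage points. With no successes both rates are 0%.

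**4. Excluding a violator.** Start from 2/11 = 18.2%. Dropping one violator gives 1/10 = 10.0% if that patient was a success and 2/10 = 20.0% if not, so the direction is open.

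**5. PFS and OS.** Kaplan-Meier handles incomplete follow-up by censoring and needs no such exclusion. A patient censored at time 0 leaves the curve unchanged, so the choice of set matters only for excluded patients with some follow-up. The documents do not settle its direction.

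**The case against.** The strongest reply is that few patients would be lost this way. Section 13 allows progression on clinical deterioration alone, and it counts non-return because of death or deterioration as progression. Clinic visits fall on Days 15 and 28 of the first three cycles, so progression can be recorded before day 84, and a patient assigned progression has arguably been evaluated. The completion scan may cover patients removed for toxicity or anticoagulation. An early leaver with a confirmed response could still be a success. This narrows the group and stands to that extent. It does not empty the group: patients who withdraw or are lost without deterioration or an exit scan remain, and Section 14 never says that the Section 13 rule satisfies its own condition. A patient with a confirmed response would be evaluated and so is not among those dropped.

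Second, 11/(11−d) compares two conventions, not an estimate with the truth. A patient taken off study for anticoagulation may have had controlled disease, and coding that patient as a failure can understate the rate. This is fair. The upward shift is shown relative to counting such patients as non-successes, which fits an endpoint that requires control to be demonstrated.

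Third, the shift is small beside intervals more than 40 points wide, and no test or threshold depends on it. Zero successes is also quite possible: from the Section 14.4 table, 1 − 0.40 = 0.60 at a true rate of 0.05 and 1 − 0.65 = 0.35 at 0.10. This limits how serious the point is, but a wide interval does not correct a shifted estimate.

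Finally, an independent radiologist reads response (Section 13), and deviations are logged within 5 days of discovery and reviewed monthly (Section 11). These limit discretion but do not restore the denominator or define a significant violation.

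**Conclusion.** The concern holds. Followed as written, the plan can drop treated patients who have no recorded success from the primary efficacy analysis, and nothing elsewhere in it puts them back. Relative to counting them as non-successes, DCR and ORR rise by a factor of 1.10 to 1.38 when 1 to 3 of 11 are dropped and there is at least one success. These sizes assume that all 11 patients are treated and that none of those dropped is a success; the number dropped and the success counts are illustrative. The upward direction is established only for unevaluated patients. It is open for violators and for PFS and OS. The plan should be corrected, but with no decision threshold and heavily overlapping intervals the point does not undermine the trial.

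**What to change.** - In Sections 14.3.3 and 14.6, make all patients who received at least one dose (the existing safety population) the set for DCR, ORR, PFS and OS.
- Count a treated patient with no qualifying assessment as a non-success for DCR and ORR. Add a line to Section 14.1 saying that this coding is not the imputation ruled out there.
- State that a patient classed as progressed under the Section 13 non-return rule counts as evaluated.
- Censor PFS at the last adequate assessment and OS at the date last known alive.
- Keep the present efficacy set as a labelled sensitivity analysis, with both of its conditions defined in advance.

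The cost is wording only; no new data are needed. The headline rate may be slightly less favourable. An amendment may be required, since Section 14.1 says: "Changes from the analysis plan will not require an amendment to the protocol unless it changes a significant feature in the protocol", and the primary efficacy population is arguably such a feature.

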## 14.4 Sample Size, Accrual and Study Duration

Our sample size is based on several considerations. For binary events, such as observing specific AEs or see at least one patient with clinical benefit (or primary efficacy objective), the following table shows the probability of seeing at least one event with a sample of size 10.

True Probability	0.05	0.10	0.15	0.20	0.25	0.30
Chance of observing $\geq 1$ Event	0.40	0.65	0.80	0.89	0.94	0.97

Thus, we will be able to see events that have a true probability of 0.15 or higher with 80% probability. Accrual should take approximately 2 years and the entire length of the study approximately 3.5 years to allow up for start-up, at least 1 year follow-up per patient, and analysis and closure.

## 14.5 Safety Analysis

The safety set will be used for all safety analysis. All safety data will be listed. For the treatment-emergent AEs, namely AEs started or worsened during the on-treatment period, the incidence will be summarized by system organ class and/or preferred term, severity based on CTCAE 5.0 grades, type of adverse event and the relation to the

study drug. Deaths reportable as SAEs and non-fatal serious adverse events will be listed by patient and tabulated by type of adverse event.

#### 14.6 Efficacy Analysis

The efficacy set will be used for all the efficacy analysis. For the primary efficacy aim of the disease control rate (CR, PR, or SD for at least 6 months), an estimate will be determined along with the corresponding exact 95% binomial confidence interval. A similar analysis will be done for the secondary objective of objective response rate (CR, PR).

For PFS and OS, the median and their corresponding two-sided 95% confidence intervals will be calculated using the Kaplan-Meier method. Estimates and 95% confidence intervals will also be provided for 6 and 12 months.

A listing of the patients who used corticosteroid will be provided.

#### 14.7 Interim Analysis

No interim analysis will be performed.

### 15 Privacy/Confidentiality Issues

An informed consent shall be used prior to initiating any treatments. The informed consent shall be approved by the Indiana University Institutional Review Board prior to the initiation of any treatments.

Study data will be entered into a password protected database. All institutional policies regarding protected health information will be followed.

## 15.1 Ethical aspects

### 15.1.1 Local Regulations

The study must fully adhere to the principles outlined in “Guideline for Good Clinical Practice” (GCP) ICH E6 Tripartite Guideline (January 1997). The investigator will ensure that the conduct of the study complies with the basic principles of GCP as outlined in the current version of 21 Code of Federal Regulations, subpart D, Part 312, “Responsibilities of Sponsors and Investigators” Part 50, “Protection of Human Subjects” and Part 56, “Institutional Review Boards.”

### 15.1.2 Informed Consent

It is the responsibility of the investigator, or a person designated by the investigator, to obtain written informed consent from each subject participating in this study after adequate explanation of the aims, methods, anticipated benefits, and potential hazards of the study. In the case where the subject is unable to read, an impartial witness should be present during the entire informed consent discussion. After the subject has orally consented to participation in the trial, the witness’s signature on the form will attest that the information in the consent form was accurately explained and understood.

The CRF for this study contains a section for documenting informed subject consent, and this must be completed appropriately. If new safety information results in significant changes in the risk/benefit assessment, the consent form should be reviewed and updated as necessary. All subjects (including those already being treated) should be informed of the new information, should be given a copy of the revised form, and should give their consent to continue in the study.

### 15.1.3 Institutional Review Board/Ethics Committee

This study is being conducted under a United States Investigational New Drug application or other Clinical Trial Application, as appropriate. This protocol (and any modifications) and appropriate consent procedures must be reviewed and approved by an IRB/EC. This board must operate in accordance with current local, regional, and federal regulations. The investigator will send a letter or certificate of IRB/EC approval to Exelixis (or designee) before subject enrollment and whenever subsequent modifications to the protocol are made.

#### 15.1.4 Future Use of Patient Samples

No samples for anything other than safety testing will be collected during this study.

## 16 Follow-up and Record Retention

The study will last for 60 months. Records will be stored in password protected databases. Any paper records will be stored in locked file cabinets only accessible to study staff. Records will be maintained for a minimum of 7 years after completion of study at which time they will be destroyed.

## 17 Next Steps

Phase 2 efficacy trial of cabozantinib in brain tumors has been proposed to the CNS Committee of the COG (Children's Oncology Group) Consortium who requested additional pilot response data before considering to support a larger Consortia-wide efficacy trial. Exelixis (pharmaceutical company) has expressed that the company is highly motivated to develop the drug in the pediatric solid tumor and brain tumor population to support a pediatric indication for this drug and would be supportive of an efficacy trial should the data warrant. Depending on the result of this pilot, the current most feasible plan is to pursue NIH and/or foundation grant to support a regional or national (through COG) multi-site clinical trial in this population. Patients have the option of COG phase 1 safety trials with limited availability, outside single institutional trials, or limited institution Pediatric Brain Tumor Consortium (PBTC) trials for which there is limited availability and not available in Indiana and require significant travel commitment. The goal is to have an institutionally available option for clinical trial enrollment at Riley Hospital for Children.

## Appendix I: Performance Status Scales

Karnofsky		Lansky	
Score	Description	Score	Description
100	Normal, no complaints, no evidence of disease	100	Fully active, normal.
90	Able to carry on normal activity, minor signs or symptoms of disease.	90	Minor restrictions in physically strenuous activity.
80	Normal activity with effort; some signs or symptoms of disease.	80	Active, but tires more quickly
70	Cares for self, unable to carry on normal activity or do active work.	70	Both greater restriction of and less time spent in play activity.
60	Required occasional assistance, but is able to care for most of his/her needs.	60	Up and around, but minimal active play; keeps busy with quieter activities.
50	Requires considerable assistance and frequent medical care.	50	Gets dressed, but lies around much of the day; no active play, able to participate in all quiet play and activities.
40	Disabled, requires special care and assistance.	40	Mostly in bed; participates in quiet activities.
30	Severely disabled, hospitalization indicated. Death not imminent.	30	In bed; needs assistance even for quiet play.
20	Very sick, hospitalization indicated. Death not imminent.	20	Often sleeping; play entirely limited to very passive activities.
10	Moribund, fatal processes progressing rapidly.	10	No play; does not get out of bed.

## Appendix II: Blood Pressure norms:

### Blood pressure (BP) levels for **BOYS**

Age (years)	BP Percentile	Systolic Blood Pressure, mm Hg							Diastolic Blood Pressure, mm						
		Percentile of Height							Percentile of Height						
		5th	10th	25th	50th	75th	90th	95th	5th	10t	25t	50t	75t	90t	95t
1	95th	98	99	101	103	104	106	106	54	54	55	56	57	58	58
2	95th	101	102	104	106	108	109	110	59	59	60	61	62	63	63
3	95th	104	105	107	109	110	112	113	63	63	64	65	66	67	67
4	95th	106	107	109	111	112	114	115	66	67	68	69	70	71	71
5	95th	108	109	110	112	114	115	116	69	70	71	72	73	74	74
6	95th	109	110	112	114	115	117	117	72	72	73	74	75	76	76
7	95th	110	111	113	115	117	118	119	74	74	75	76	77	78	78
8	95th	111	112	114	116	118	119	120	75	76	77	78	79	79	80
9	95th	113	114	116	118	119	121	121	76	77	78	79	80	81	81
10	95th	115	116	117	119	121	122	123	77	78	79	80	81	81	82
11	95th	117	118	119	121	123	124	125	78	78	79	80	81	82	82
12	95th	119	120	122	123	125	127	127	78	79	80	81	82	82	83
13	95th	121	122	124	126	128	129	130	79	79	80	81	82	83	83
14	95th	124	125	127	128	130	132	132	80	80	81	82	83	84	84
15	95th	126	127	129	131	133	134	135	81	81	82	83	84	85	85
16	95th	129	130	132	134	135	137	137	82	83	83	84	85	86	87
≥17	95th	131	132	134	136	138	139	140	84	85	86	87	87	88	89

Instructions for using this BP Chart:

1. Measure the patient's blood pressure using an appropriate size cuff.
2. Select appropriate chart for a female or male patient.
3. Using the "age" row and "height" column determine if the BP is within the ULN.

This table was taken from "The Fourth Report on the Diagnosis, Evaluation, and Treatment of High Blood Pressure in Children and Adolescents" PEDIATRICS Vol. 114 No. 2 August 2004, pp. 555-576.

